## 1. Protocol Synopsis

**Title of Study:** A Randomized, 9-Way, Single-Dose, Crossover Study to Evaluate the Pharmacokinetics, Pharmacodynamics, Safety, and Tolerability of LY3185643 and rGlucagon in Healthy Subjects

**Rationale:** The availability of insulin pumps and continuous glucose monitors has transformed diabetes care by allowing continuous infusion of insulin with bolus doses administered based on food intake. Hypoglycemia may result from excessive insulin administration in relation to food intake, disease state, or physical activity.

Hypoglycemia may be life-threatening; this is a risk with any insulin administration, and may be of concern with automated systems.

An artificial pancreas device system (APDS) may provide better control of blood sugar with less episodes of hypoglycemia. A bihormonal APDS combines automated delivery of both insulin and glucagon. Pilot studies using investigational, bihormonal APDSs have demonstrated that delivery of small doses of glucagon in response to declining glucose levels reduces the frequency of hypoglycemia. Glucagon opposes the effects of insulin in the liver and increases blood glucose levels.

The current commercial glucagon (recombinant glucagon [rGlucagon]) preparations are only available as lyophilized powder that must be reconstituted with a diluent before administration. The current Lilly formulation of rGlucagon also has poor solubility in aqueous buffers at or near physiological pH values and poor chemical and physical stability when formulated at low and high pH.

LY3185643 is a glucagon analog with improved solubility that is being developed for use in a bihormonal APDS. The current study is designed to assess the pharmacokinetic (PK) and pharmacodynamic (PD) profiles of LY3185643 and compare these to rGlucagon.

**Objectives/Endpoints:**

Primary Objective	Endpoints
The primary objective of this study is to evaluate the PK and PD profiles of LY3185643 and rGlucagon after single doses of study treatment	$C_{max}$ , AUC, and terminal half-life of LY3185643 and rGlucagon $C_{max}$ and AUC (change from predose) of blood glucose and C-peptide
Secondary Objective	Endpoints
To evaluate the safety and tolerability of LY3185643 after single doses of study treatment	Adverse events

Abbreviations: AUC = area under the concentration versus time curve;  $C_{max}$  = maximum concentration;

PD = pharmacodynamic; PK = pharmacokinetic; rGlucagon = recombinant glucagon.

**Summary of Study Design:** This study is a Phase 1, single-center, subject- and investigator-blind, randomized, 9-way, 3-period crossover study in healthy subjects to evaluate the PK and PD of LY3185643 and rGlucagon after subcutaneous (SC) administration.

Up to 37 healthy men and women may be enrolled to target approximately 18 subjects to complete the study. Each subject will receive 3 doses on each of 3 dosing days (total of 9 doses: 5 doses of LY3185643 and 4 doses of rGlucagon) administered SC. Doses will be administered in a 9-way complete crossover design in 3 periods, and subjects will be randomized to predefined treatment sequences.

Each study period will consist of 3 days (Days -1 to 2). Subjects should return for the next period with a minimum of 3 days between treatment periods.

Blood samples will be collected for the determination of concentrations of LY3185643, glucagon, glucose, C-peptide, and for immunogenicity. Safety data will include clinical examinations, vital signs, electrocardiograms (ECGs; including telemetry), clinical laboratory tests, and a record of adverse events (AEs).

**Treatment Arms and Duration:** Each subject will be randomized to 1 of 9 treatment sequences comprising single SC doses of LY3185643 or rGlucagon. Subjects will receive 9 doses total during 3 treatment periods (3 doses per period). Each treatment period will consist of 3 days with a minimum of 3 days between each period. A follow-up visit will be required at least 30 days after completing the last dose of study treatment.

**Number of Subjects:** Up to 37 subjects may be enrolled so that approximately 18 subjects complete the study.

**Statistical Analysis:** PK and PD analyses will be conducted on the full analysis set. This set includes all data from all randomized subjects receiving at least 1 dose of the investigational product and with a baseline and at least 1 postbaseline measurement for each dose according to the treatment the subjects actually received. Safety analyses will be conducted for all enrolled subjects whether or not they completed all protocol requirements.

**Sample Size:** The sample size is customary for Phase 1 studies evaluating safety, PK, and/or PD parameters and is considered sufficient to evaluate the primary objective of this study.

**Safety:** All investigational product and protocol procedure AEs will be listed, and if the frequency of events allows, safety data will be summarized using descriptive methodology. Other safety parameters that will be assessed include safety laboratory parameters, vital signs, and ECG parameters. The safety parameters will be listed and summarized using standard descriptive statistics.

**Pharmacokinetics:** PK parameter estimates for LY3185643 and rGlucagon will be calculated by standard noncompartmental methods of analysis. The primary parameters for analysis will be maximum drug concentration ( $C_{max}$ ) and area under the concentration versus time curve (AUC). Other noncompartmental parameters, such as half-life, apparent clearance, and apparent volume of distribution, may be reported. Population PK and exposure-response analyses may be performed using PK and glucose data.

PK parameters for LY3185643 and rGlucagon will be summarized for each dose group. PK parameter estimates will be evaluated to delineate effects of dose proportionality.

**Pharmacodynamics:** The PD time-action and response of LY3185643 and rGlucagon will be compared to establish the relative potency between LY3185643 and rGlucagon. The primary PD response variables of interest include time to  $C_{max}$  ( $T_{max}$ ),  $C_{max}$ , and change from baseline to each time point, and incremental AUCs for glucose and C-peptide. A dose-proportionality parameter will also be estimated to establish the relative potency between LY3185643 and rGlucagon. Partial AUC for glucose over appropriate time intervals will be calculated using the trapezoidal rule.

Parameters will be analyzed using a nonlinear mixed-effects model with period, treatment (LY3185643 or rGlucagon), and dose (within treatment) as fixed effects, baseline glucose as a covariate, and subject as a random effect. A conversion factor will be defined in the model for each parameter to estimate the relative potency of LY3185643 to rGlucagon. In addition, a conversion factor will be estimated between LY3185643 and rGlucagon

for multiple parameters simultaneously using a similar mixed nonlinear model approach to account for the correlation between parameters for the same subject.

All PD parameters including the baseline-corrected parameters will be summarized by dose group and tabulated. Summary statistics will be provided. The individual observed and mean (by dose group) time profile of the PD measurements after dosing will be plotted.

Immunogenicity: The frequency of antibody formation to LY3185643 will be determined. If a neutralization assay is performed, the frequency of neutralizing antibodies will be determined. The relationship between the presence (or absence) of antibodies and AEs will be assessed. Likewise, the relationship between the presence of antibodies and the PK parameters and PD response to LY3185643 will be assessed.

Interim Analysis: No interim analyses are planned for this study.

The Lilly study team is unblinded, and the investigator will remain blinded until the study is completed. Data may be analyzed while the trial is ongoing, but no changes to the study design are planned. An assessment committee will not be formed.

## 2. Schedule of Activities

## Study Schedule Protocol I8Z-MC-APCA

Procedure	Screen	Periods 1, 2, 3 a			FU/ET b	Comments
	Up to Day -28	Day -1	Day 1 c	Day 2		
Informed consent	X					
Admission to CRU		X				
Discharge from CRU				X		
Carbohydrate-rich meal		X				Subjects will be provided a meal approximately 10:00 PM and will remain fasted until completion of the study procedures on Day 1.
Treatment administration			X (3 doses)			Subjects will receive 3 doses of study treatment, each separated by at least 4 hours (for example, 8:00 AM, 12:00 PM, 4:00 PM).
Medical history	X					
Height	X					
Weight	X	X			X	
AEs/concomitant medications	X		X	X	X	Collected throughout the study.
Vital signs (minutes)	X		-20 ( $\pm 10$ ), 15 ( $\pm 5$ ), 30 ( $\pm 5$ ), 45 ( $\pm 5$ ), 60 ( $\pm 5$ ), 90 ( $\pm 15$ ), 120 ( $\pm 15$ ), 180 ( $\pm 15$ ), 210 ( $\pm 15$ )	X	X	Supine blood pressure and/or pulse rate may be measured as clinically indicated. Sampling times are relative to the time of each study drug administration.
Clinical laboratory tests	X		Any time before the first dose		X	Period 1 only. See Appendix 2 , Clinical Laboratory Tests, for details.
Pregnancy test	X	X			X	Urine pregnancy tests will be performed. See Appendix 2 , Clinical Laboratory Tests, for details.
Physical examination/medical assessment	X			X	X	Physical examination at screening. Thereafter, medical assessment and targeted examination, as appropriate.
12-lead ECG (minutes)	X		-20 ( $\pm 10$ )		X	Single ECGs will be collected for safety. Predose ECGs must be recorded before collecting any blood for safety or PK tests.
ECG telemetry		X	X			The ECG waveform and cardiac rhythm will be monitored continuously using an ECG telemetry monitor during the inpatient stay at the CRU, from the night of Day -1 to 4 hours after the last dose on Day 1 for all 3 periods.

## Study Schedule Protocol I8Z-MC-APCA

Procedure	Screen	Periods 1, 2, 3 a			FU/ET b	Comments
	Up to Day -28	Day -1	Day 1 c	Day 2		
Continuous ECG monitoring			X			15 ECGs will be extracted from the continuous ECG recording at -5, 30, 60, 120, and 180 minutes postdose for each Day 1 dose administration.
PK samples: LY3185643 or glucagon (minutes)			0 (predose), 15 ( $\pm 2.5$ ), 30 ( $\pm 2.5$ ), 60 ( $\pm 5$ ), 120 ( $\pm 10$ ), 180 ( $\pm 10$ )			Sampling times are relative to the time of each study drug administration.
Glucose samples (minutes)			-5 ( $\pm 2.5$ ), 0 (predose), 5 ( $\pm 1$ ), 10 ( $\pm 1$ ), 15 ( $\pm 2.5$ ), 22 ( $\pm 2.5$ ), 30 ( $\pm 2.5$ ), 45 ( $\pm 5$ ), 60 ( $\pm 5$ ), 75 ( $\pm 5$ ), 90 ( $\pm 5$ ), 105 ( $\pm 5$ ), 120 ( $\pm 5$ ), 150 ( $\pm 5$ ), 180 ( $\pm 5$ )			Blood concentrations using YSI glucose analyzer. Sampling times are relative to the time of each study drug administration.
PD samples: C-peptide, glucose (minutes)			-5 ( $\pm 2.5$ ), 0 (predose), 5 ( $\pm 1$ ), 15 ( $\pm 2.5$ ), 30 ( $\pm 2.5$ ), 60 ( $\pm 5$ ), 120 ( $\pm 5$ )			Sampling times are relative to the time of each study drug administration.
Immunogenicity (LY3195643 antibodies) samples			Any time before the first dose		X	Period 1 and Period 3 only. Prior to the first dose only.

Abbreviations: AE = adverse event; CRU = clinical research unit; ECG = electrocardiogram; ET = early termination; FU = follow-up; PD = pharmacodynamics; PK = pharmacokinetics.

Note: The site should schedule activities as appropriate. In cases where several study procedures are scheduled at the same time, the order of priority for these procedures will be as follows: PK samples, PD samples, vital signs, ECG, clinical laboratory samples.

a Each treatment period will consist of 3 days (Days -1 to 2). Subjects should return for the next period with a minimum of 3 days between treatment periods.

b FU/ET visit will occur at least 30 days after completing the last dose of study treatment.

c Study drug will be administered 3 times on Day 1 in each period. Day 1 activities will be performed 3 times on Day 1 with the sampling times corresponding to each study drug administration.

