### 3. Introduction

#### 3.1. Study Rationale

The Diabetes Control and Complications Trial (DCCT) and its observational Epidemiology of Diabetes Interventions and Complications (EDIC) follow-up study demonstrated that intensive therapy (that lowers glycemia) reduced renal and cardiovascular disease, the predominant causes of early mortality in patients with type 1 diabetes mellitus (T1DM) (Nathan et al. 2005; DCCT/EDIC Research Group et al. 2011).

The availability of insulin pumps and continuous glucose monitors has transformed diabetes care by allowing continuous infusion of insulin with bolus doses administered based on food intake. Hypoglycemia may result from excessive insulin administration in relation to food intake, disease state, or physical activity. Hypoglycemia may be life-threatening; this is a risk with any insulin administration, and may be of concern with automated systems.

An artificial pancreas device system (APDS) may provide better control of blood sugar with less episodes of hypoglycemia. A bihormonal APDS combines automated delivery of both insulin and glucagon. Pilot studies using investigational, bihormonal APDSs have demonstrated that delivery of small doses of glucagon in response to declining glucose levels reduces the frequency of hypoglycemia (Russell et al. 2012). Glucagon is a 29-aminoacid peptide hormone produced in the pancreas that stimulates glucagon receptors in the liver, resulting in the breakdown of stored glycogen into glucose. Glucagon opposes the effects of insulin in the liver and increases blood glucose levels.

The current commercial glucagon (recombinant glucagon [rGlucagon]) preparations are only available as lyophilized powder that must be reconstituted with a diluent before administration. The current Lilly formulation of rGlucagon also has poor solubility in CCI [REDACTED]

LY3185643 is a glucagon analog with improved solubility that is being developed for use in a bihormonal APDS. The current study is designed to assess the pharmacokinetic (PK) and pharmacodynamic (PD) profiles of LY3185643 and compare these to rGlucagon. Understanding the relative potency of these molecules, as well as any differences in time-action profiles, will be used to direct modifications of APDS control algorithms that have been developed based on rGlucagon pharmacology. These modified control algorithms will be tested in future studies using LY3185643 in an investigational, bihormonal APDS.

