### **3.2.1. Clinical Experience**

LY3185643 has been administered SC to 27 healthy subjects as single doses of 0.01 mg, 0.03 mg, 0.05 mg, 0.06 mg, 0.1 mg, 0.2 mg, 0.3 mg, 0.48 mg, and 0.72 mg (n = 3 subjects for each dose level). Preliminary PK data available for doses up to 0.2 mg show dose-dependent increases in LY3185643 exposures. Over the dose range of 0.01 to 0.2 mg, the median time to peak concentrations ranged between 0.5 to 1.25 hours, mean peak concentrations ranged between 0.13 to 4.25 ng/mL, and mean terminal  $t_{1/2}$  ranged between 0.5 to 0.75 hours. LY3185643 concentrations decreased below the limit of quantification by 4 hours postdose. Dose-dependent increases in glycemic response were observed up to 0.2-mg dose level. Maximum mean blood glucose elevations of up to 180 mg/dL were observed at doses above 0.2 mg of LY3185643. Peak glucose concentrations were reached between 0.5 to 2 hours postdose, and glycemic effects lasted for up to 3 hours postdose. This transient glycemic effect at high LY3185643 concentrations is consistent with rGlucagon findings and likely reflects a feedback inhibition of hepatic glucose output in response to exogenous glucagon administration (Mighiu et al. 2013).

Adverse events (AEs) included nausea, vomiting, light headed, headache, dizziness, vasovagal episode, erythema at injection site, loose stools, feeling hot and cold, abrasion of right leg, increased appetite, right thigh ache, drowsiness, feels sleepy, feels faint, decreased alertness, and dehydration. The most common (67% of 36 reported events) AEs were nausea (n=10), vomiting (n=6), headache (n=3), dizziness (n=3), and light headedness (n=2). No serious AEs (SAEs) were noted.

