**Table APCA.4.1. Objectives and Endpoints**

Primary Objective	Endpoints
The primary objective of this study is to evaluate the PK and PD profiles of LY3185643 and rGlucagon after single doses of study treatment	$C_{max}$ , AUC, and terminal half-life of LY3185643 and rGlucagon $C_{max}$ and AUC (change from predose) of blood glucose and C-peptide
Secondary Objective	Endpoints
To evaluate the safety and tolerability of LY3185643 after single doses of study treatment	Adverse events
Exploratory Objective	Endpoints
To evaluate immunogenicity of LY3185643 after multiple single doses of study treatment	Anti-LY3185643 antibodies

Abbreviations: AUC = area under the concentration versus time curve;  $C_{max}$  = maximum concentration;

PD = pharmacodynamic; PK = pharmacokinetic; rGlucagon = recombinant glucagon.

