## 5.4. Scientific Rationale for Study Design

A population of healthy subjects is selected based upon the likelihood of less physiologic variability in the absence of disease states that may affect multiple organ systems and the absence of other confounding factors such as concomitant medications. Furthermore, studies with native glucagon suggest that the PD responses being assessed in this study are similar between healthy subjects and subjects with diabetes who form the eventual patient population for this treatment (Nielsen et al. 1997; Matsuda et al. 2002).

Three doses of LY3185643 and/or rGlucagon will be administered on Day 1 of each study period; each dose will be separated by at least 4 hours. A 4-hour dosing cycle is considered appropriate because previous clinical data support that a 4-hour observation period is a sufficient amount of time to obtain both the PK and PD profiles. The study drug concentrations will be below the quantification limits by 4 hours and the glycemic levels will return back to baseline within 4 hours postdose. A previous study used a similar design with up to 4 doses given over the course of a single day and showed that this dosing schedule was well tolerated and that the PD response was not attenuated or refractory to repeat dosing (Blauw et al. 2016).

The use of a crossover design allows each subject to serve as his or her own control, thereby reducing variability.

The currently marketed glucagon product, rGlucagon, will be administered to provide a comparison of its PK/PD profile to the PK/PD profile of LY3185643.

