### **10.3.3.1. Pharmacodynamic Parameter Estimation**

The primary PD response variables of interest include  $T_{max}$ ,  $C_{max}$ , and change from baseline to each time point, and incremental AUCs for glucose and C-peptide. A dose-proportionality parameter will also be estimated to establish the relative potency between LY3185643 and rGlucagon. Partial AUC for glucose over appropriate time intervals will be calculated using the trapezoidal rule. The AUC for each subject after each dose will also be baseline-adjusted. Baseline for each dose will be defined as the average of predose values for that dose.

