#### ***10.3.5. Interim Analyses***

No interim analyses are planned for this study. If an unplanned interim analysis is deemed necessary, the Lilly clinical pharmacologist, CRP/investigator, or designee will consult with the appropriate medical director or designee to determine if it is necessary to amend the protocol.

The Lilly study team is unblinded, and the investigator will remain blinded until all data collection has been completed. Data may be analyzed while the trial is ongoing, but no changes to the study design are planned. An assessment committee will not be formed.

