**Protocol I8Z-MC-APCA Sampling Summary**

Purpose	Maximum Blood Volume per Sample (mL)	Maximum Number of Blood Samples	Maximum Total Volume (mL)
Screening tests a	17	1	17
Clinical laboratory tests a	11	2	22
Pharmacokinetics	4	54	216
Blood discard for cannula patency	0.25	135	33.75
Pharmacodynamics (glucose)	0.2	135	27
Pharmacodynamics (glucose and C-peptide)	2.5	63	157.5
Immunogenicity	7	3	21
Total			494.25
Total for clinical purposes [rounded up to nearest 10 mL]			500

a Additional samples may be drawn if needed for safety purposes.

---

**Appendix 6. Protocol Amendment I8Z-MC-APCA(a)  
A Randomized, 9-Way, Single-Dose, Crossover Study to  
Evaluate the Pharmacokinetics, Pharmacodynamics,  
Safety, and Tolerability of LY3185643 and rGlucagon in  
Healthy Subjects**

---

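### Does the missing AUC end time, with C-peptide sampled to 120 min and YSI glucose to 180 min, undermine the conversion factor?

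*Protocol*

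**What the plan says.** Protocol Table APCA.4.1 lists among the primary endpoints the Cmax and "AUC (change from predose) of blood glucose and C-peptide", with no time limit.

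The Schedule of Activities (Protocol section 2) fixes the samples after each dose:

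- C-peptide and laboratory glucose, from one tube, in the row that begins "PD samples: C-peptide, glucose (minutes": −5, 0, 5, 15, 30, 60 and 120 min.
- YSI glucose: −5, 0, 5, 10, 15, 22, 30, 45, 60, 75, 90, 105, 120, 150 and 180 min.

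On AUC, Protocol 10.3.3.1 and SAP 9.4.1 name incremental AUCs of glucose and C-peptide among the primary PD variables. Protocol 10.3.3.1 then adds: "Partial AUC for glucose over appropriate time intervals will be calculated using the trapezoidal rule". SAP 9.4.2 repeats this for glucose as an addition to the modelled parameters, and SAP 9.4.3 extends it to laboratory glucose and C-peptide. SAP 9.4.1 also plans the same response variables for laboratory glucose.

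SAP 9.4.2 fits, for each PD parameter, a model linear in dose and reports λ = β1/(β1 + β2) with a 90% confidence interval. λ is the LY3185643 dose equivalent to one unit of rGlucagon.

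**The concern.** Two primary AUCs appear to be measured over different spans, and the span is written down for neither. Protocol 5.4 defends the dosing cycle on the ground that "previous clinical data support that a 4-hour observation period is a sufficient amount of time to obtain both the PK and PD profiles", yet C-peptide stops at 2 h with no reason given. Protocol 3.2.1 reports of the earlier study: "Peak glucose concentrations were reached between 0.5 to 2 hours postdose, and glycemic effects lasted for up to 3 hours postdose". Part of a C-peptide response could therefore lie beyond the last tube.

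A ratio of AUCs is free of the window only if both drugs have the same time course. Protocol 3.1 leaves that open: "Understanding the relative potency of these molecules, as well as any differences in time-action profiles" is given as something the study should supply to guide the device algorithms. If one drug acts later, a shorter window makes it look weaker. The λ values from C-peptide and from YSI glucose could then disagree merely because their windows differ, and Protocol 10.3.3.2 plans a joint factor over several parameters.

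There is also a pre-specification worry. Protocol 10.3.5 says "The Lilly study team is unblinded, and the investigator will remain blinded until all data collection has been completed" and allows analysis during the trial, so an unnamed window could be picked with results by treatment in view.

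**Working it through.** **1. The schedule is as intended.** Nine doses per subject give 7 × 9 = 63 C-peptide/laboratory-glucose samples and 15 × 9 = 135 YSI samples. Both match Protocol Appendix 5, so the 120-min and 180-min end points are the design and not a misprint.

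**2. What λ becomes.** Suppose responses are noise-free and proportional to dose, with AUC per unit dose a_R for rGlucagon and a_L for LY3185643. Then β1 = a_R and β1 + β2 = a_L, so λ = a_R / a_L.

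**3. Triangular illustration (assumed shapes).** Each response rises linearly to a peak at p and falls to zero at e, in minutes. Both drugs have the same total AUC, so the full-curve λ is 1.00. For e above 120, the share of AUC lying after 120 min is (e − 120)² / [(e − p) e].

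- rGlucagon p = 60, e = 180: 3600/21600 = 0.1667 after, 0.8333 by 120 min.
- LY3185643 p = 75, e = 180: 3600/18900 = 0.1905 after, 0.8095 by 120 min.
- LY3185643 p = 90, e = 180: 3600/16200 = 0.2222 after, 0.7778 by 120 min.
- rGlucagon p = 60, e = 150: 900/13500 = 0.0667 after, 0.9333 by 120 min.

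| rGlucagon (p, e) | LY3185643 (p, e) | λ, 0–180 | λ, exact 0–120 | λ, C-peptide times 0–120 |
|---|---|---|---|---|
| 60, 180 | 60, 180 | 1.00 | 1.00 | 1.00 |
| 60, 180 | 75, 180 | 1.00 | 0.8333/0.8095 = 1.029 | 1.151 |
| 60, 180 | 90, 180 | 1.00 | 0.8333/0.7778 = 1.071 | 1.250 |
| 60, 150 | 60, 180 | 1.00 | 0.9333/0.8333 = 1.120 | 1.120 |

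Reversing the drugs in the two peak-shift rows gives 0.971 and 0.933 on 0–120 min.

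**4. Where 1.151 and 1.250 come from.** Set the peak height to 1. The C-peptide trapezoid has no point between 60 and 120 min.

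- rGlucagon (60, 180): 30 up to 60 min, plus 60 × (1 + 0.5)/2 = 45, total 75. This is exact.
- LY3185643 (75, 180): 24 + 60 × (0.8 + 0.5714)/2 = 65.14, against an exact 72.86. So 75/65.14 = 1.151, which is 1.029 from the window times 72.86/65.14 = 1.118 from the sampling gap.
- LY3185643 (90, 180): 20 + 40 = 60, against an exact 70. So 75/60 = 1.250, which is 1.071 from the window times 70/60 = 1.167 from the gap.

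In these cases most of the C-peptide excess comes from the missed peak between 60 and 120 min. Naming an end time would not alter it.

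**5. A slower-decaying shape (assumed).** With response (t/tp²)·exp(−t/tp), peak at tp and equal total AUC, and rGlucagon peaking at 30 min, λ on the YSI times is:

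| LY3185643 peak (min) | λ, 0–120 | λ, 0–180 | LY3185643 response after 180 min |
|---|---|---|---|
| 30 | 1.00 | 1.00 | 1.7% |
| 37.5 | 1.10 | 1.03 | 4.8% |
| 45 | 1.22 | 1.08 | 9.2% |
| 60 | 1.53 | 1.23 | 19.9% |

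The two windows differ by about 6%, 13% and 24% in the last three rows. For the 45-min case the C-peptide times give 1.26 against 1.22, so here the window matters more than the gap. The larger effects need a sizeable response after 3 h, which fits poorly with the duration reported in Protocol 3.2.1.

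**6. Would a longer C-peptide window help?** A 180-min tube adds 9 × 2.5 = 22.5 mL, taking the 494.25 mL in Appendix 5 to 516.75 mL. That exceeds the 500 mL in the line "Total for clinical purposes [rounded up to nearest 10 mL]". Assume independent errors of equal SD and a baseline equal to the mean of the −5 and 0 min values. The SD of the baseline-adjusted AUC per unit error SD is then √10550 = 102.7 for 0–120 min and √23000 = 151.7 for 0–180 min, about 48% more. If a triangular response ends at 125–145 min, the 0–180 AUC is further from the truth in 15 of 20 cases tried.

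**The case for a change.** The strongest case for a change is that the remedy costs a sentence or two in the SAP, that primary endpoints should carry their time limits, and that the sponsor's team is unblinded. The facts behind it are right: no end time is stated, and step 5 shows that λ can move by more than the triangles suggest.

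Less of it survives a close reading. The wording about suitable intervals belongs to the partial AUCs, which are additional summaries. The primary incremental AUCs are listed separately, and the ordinary reading is the sampled interval. That leaves two fixed windows, not a free choice; a 0–60 min window, which gives the most extreme ratios, is named nowhere. SAP section 3 requires sign-off before first dosing and refers to table shells that were not available here and may state the windows. λ has no success threshold that a choice of window could cross.

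Adding a YSI 0–120 min AUC would not make the two analytes comparable: in the triangles it gives 1.03 and 1.07 against 1.15 and 1.25 for C-peptide, because the sampling times still differ. Laboratory glucose, already planned, matches C-peptide on both counts.

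If time courses do differ, no window yields the one true λ, and a joint factor is a compromise under any of them. The planned tmax, change from baseline at each time point and profile plots show such a difference directly.

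**Conclusion.** No change is needed. The missing end time is a detail that an analyst following the schedule would fill in one sensible way: 0–120 min for C-peptide and laboratory glucose, 0–180 min for YSI glucose. Stopping C-peptide at 120 min is a fair trade-off against blood volume and noise.

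On size, the window has no effect on λ if the time courses are equal. Between 0–120 and 0–180 min it is worth 3–7% for triangular responses with peaks shifted by 15–30 min, and 12% if the drugs' effects end at 150 and 180 min. It is larger for slowly decaying curves.

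All of these figures rest on assumed shapes, equal total AUC, and responses proportional to dose without noise. The documents give no C-peptide time course and no comparison of timing between the drugs in humans. The nonclinical glucose timing in Protocol 3.2 was similar for both, and the 3 h figure in Protocol 3.2.1 concerns glucose in a study with doses up to 0.72 mg, against a top dose of 0.2 mg here. Loss of C-peptide response after 120 min is therefore possible but not shown.
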